4.0 OBJECTIVES

4.1 Primary Objectives

The primary objective of the trial is to evaluate the effect of the potent CYP3A4 inhibitor itraconazole on the single-dose PK of TAK-954.

4.2 Secondary Objectives

The secondary objectives of the trial are to evaluate the safety of single-dose IV doses of TAK-954 in the presence and absence of a potent CYP3A4 inhibitor.

4.3 Exploratory Objectives

Exploratory objectives of this trial include:

CCI

4.4 Study Design

This is a phase 1, single-sequence, open-label, 2-period crossover trial in approximately 10 healthy male and female (non-childbearing potential) subjects. The trial is designed to investigate the effect of a potent CYP3A4 inhibitor (itraconazole) on the PK of TAK-954. TAK-954 0.2 mg will be administered as a single 60-minute IV infusion.

The trial will include a Screening Visit, Trial Period 1 (6 days), a washout (a minimum of 7 days between doses in Period 1 Day 1 and Period 2 Day 1), Trial Period 2 (9 days), and a Follow-up Visit.

On Day 1 of Trial Period 1 subjects will receive a 0.2 mg single-dose TAK-954 IV on this day and on Day 4 of Trial Period 2 at approximately the same time (between 0600 and 0900). In Trial Period 2, subjects will receive 200 mg QD itraconazole orally on Days 1 to 8 at approximately the same time (between 0600 and 0900). Itraconazole will be administered as 2 x 100 mg capsules.

Blood samples for assessment of TAK-954 concentrations will be collected before each dose of TAK-954 and at intervals up to 120 hours after the last dose of trial drug in each trial period. Samples may be assayed for TAK-954 metabolites. TAK-954 and its metabolites will also be assayed in urine, data permitting and if deemed possible.

Whole blood samples for DNA PGx analysis and RNA isolation will be collected predose on Day 1 of Trial Period 1.

Safety will be assessed by monitoring for AEs, ECGs, vital signs, safety laboratory tests, and physical examinations throughout each dosing period.

CCI

After completion of the trial (or after subject withdrawal), all subjects will return for a Follow-up Visit, approximately 10 to 14 days after their last dose of trial drug.

5.0 ANALYSIS ENDPOINTS

The primary endpoint of the trial is the following PK parameters on Day 1 of Trial Period 1 and Day 4 of Trial Period 2:

- Maximum observed concentration (C_{\max}).
- Area under the concentration-time curve from time 0 to infinity, calculated using the observed value of the last quantifiable concentration (AUC_{∞}).

[figure not shown]
Safety endpoints include the following:

Safety and tolerability will be assessed through physical examinations, ECGs, vital signs, and laboratory assessments, and collection of spontaneous AEs.

Exploratory endpoints will be assessed through the following parameters:

[figure not shown]
PK parameters:

CCI

Pharmacodynamic parameters:

CCI

6.0 DETERMINATION OF SAMPLE SIZE

Approximately 10 subjects will complete this trial. With this sample size, a 2-sided 95.0% CI for the geometric mean ratio of Cmax for TAK-954 when administered with and without itraconazole will have 90% probability of excluding 1.25 (the upper bound of the bioequivalence range) if itraconazole increases the Cmax for TAK-954 by at least 50%. This calculation assumes that the CI is based on the t statistic, that the distance from the mean to the lower bound of the CI on the natural-log scale is 0.182, and that the true SD of differences on the natural-log scale is 0.187 as estimated from Cmax values reported for Cohort 1 in Theravance Protocol No. 0095. Assuming the intrasubject variation observed for area under the concentration-time curve from time 0 to time t in that cohort (SD=0.129), a 2-sided 95.0% CI for the geometric mean ratio of AUC_∞ for TAK-954 when administered with and without itraconazole will have greater than 99% probability of excluding 1.25 if itraconazole increases AUC_∞ for TAK-954 by at least 50%.

Subjects who drop out may be replaced at the discretion of the sponsor in consultation with the investigator. Subjects who replace dropouts will begin the trial as a new subject in Trial Period 1.

7.0 METHODS OF ANALYSIS AND PRESENTATION

7.1 General Principles

Continuous data will be summarized using descriptive statistics, including the number of subjects, mean, standard deviation (SD), median, minimum, and maximum. The coefficient of variation (%CV) and geometric mean will be included in the summary of continuous data where indicated. Categorical data will be summarized as the number and percentage of subjects in each category.

Arithmetic means, geometric means, and medians will be presented to 1 more decimal place than the recorded data, and SDs will be presented to 2 more decimal places than the recorded data, where appropriate. Where applicable, confidence intervals about a parameter estimate will be presented using the same number of decimal places as the parameter estimate and p-values will be rounded to 3 decimal places prior to assessment of statistical significance.

All study-related raw data for enrolled subjects, including derived data, will be presented in data listings. In addition, the actual day relative to the first dose will be presented, where applicable.

All statistical analyses will be performed using the SAS System® Version 9.4.

7.1.1 Study Definitions

There are no study-specific definitions.

7.1.2 Definition of Study Days

Study Day 1 is defined as the date of the first dose of study drug, as recorded on the electronic case report form (eCRF) dosing page. Other study days are defined relative to Study Day 1, with Day 1 being Study Day 1 and Day -1 being the day prior to Study Day 1. Study days prior to the first dose of study drug will be calculated as: {date of assessment/event – date of first dose of study drug}. Study days on or after the first dose of study drug will be calculated as: {date of assessment/event – date of first dose of study drug + 1}.

7.1.3 Definition of Study Visit Windows

There will be no visit windowing.

7.1.4 Conventions for Missing Adverse Event Dates

There will be no imputation of incomplete or missing adverse event dates.

7.1.5 Conventions for Missing Concomitant Medication Dates

There will be no imputation of incomplete or missing concomitant medication dates.

7.1.6 Conventions for Missing Data

There will be no imputation of incomplete or missing data.

Plasma concentrations that are below the lower limit of quantification (< LLOQ) will be treated as zero in the summarization of concentration values and derivation of PK parameters.

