6.2 Rationale for Trial Design, Dose, and Endpoints

6.2.1 Rationale of Trial Design and Dose

TAK-954 is a small molecule, 5-HT4 agonist. TAK-954 has been investigated in healthy subjects at single oral doses from 0.1 to 20 mg, multiple oral doses from 0.2 to 10 mg once daily (QD) for 10 days, and multiple IV doses from 0.1 to 0.5 mg QD for 5 days. A single IV dose of 0.5 mg TAK-954 has also been investigated in critically ill patients with enteral feeding intolerance and compared with metoclopramide. After multiple IV infusion dosing in healthy subjects (0.1 and 0.5 mg with a 1-hour infusion), TAK-954 concentrations declined in a biphasic manner, with mean $t_{1/2}$ values ranging from 18.0 to 18.9 hours on Day 5. TAK-954 steady state was achieved by Day 3 with minimal accumulation of TAK-954 after multiple IV dosing of 0.5 mg. The increase in exposure from the 0.1 mg to 0.5 mg IV dose was approximately dose proportional, and the mean amount of TAK-954 excreted unchanged in urine on Day 5 ranged from 27.7% to 31.6%. In subjects who were critically ill and received 0.5 mg by IV infusion, the PK exposure was slightly lower relative to that observed in healthy subjects.

Two active metabolites were identified nonclinically, but TAK-954 was not extensively metabolized to either of these metabolites after oral dosing (mean C_{max} and area under the concentration-time curve from time 0 to 48 hours metabolite to parent ratios ranged from 0.0008 to

0.004). Renal excretion of these metabolites was also low with concentrations in urine generally below the limit of detection. Evidence of GI prokinetic activity in healthy subjects (increased bowel movement frequency, looser stool consistency, and decreased time to first bowel movement) was observed at all dose levels after receiving single and multiple doses (oral and IV). In 7 subjects who were critically ill, scintigraphy data qualitatively suggest TAK-954 decreases gastric emptying time after a liquid meal.

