7.9 Pharmacokinetic/Pharmacodynamic Analysis

7.9.1 Pharmacokinetic Analysis

Blood samples for PK analysis of TAK-954 are obtained relative to the dose on Day 1 of Period 1 and Day 4 of Period 2 at the following times: predose (within 30 minutes), and 0.33, 0.5, 0.67, 1 (just after the end of infusion), 1.5, 2, 3, 4, 6, 12, 24, 36, 48, 72, 96, and 120 hours postdose (relative to TAK-954 start of infusion).

The concentration of TAK-954 (and metabolites THRX-513466 and THRX-913682) in plasma will be summarized by regimen over each scheduled sampling time point using descriptive statistics (arithmetic mean, SD, CV%, median, minimum and maximum). Individual plasma concentration data versus time will be presented in a data listing.

In addition, the figures for mean plasma concentrations of TAK-954 (and any measured metabolites) versus time (linear and semi-log scale) will be generated.

Urine is collected at predose, 0 to 6, 6 to 12, 12 to 24, and 24 to 48 hours relative to TAK-954 infusion start in Trial Periods 1 and 2. The amount of TAK-954 (and any measured metabolites) recovered in urine will be summarized by regimen over each scheduled sampling interval using descriptive statistics (arithmetic mean, SD, CV%, median, minimum and maximum). Individual urine collection information including volume, concentration, and amount recovered will be presented in a data listing.

The plasma PK parameters determined are C_{max} , AUC_{∞} , AUC_{last} , $t_{1/2}$, CL, and V_z . The ratio of metabolite parameter to TAK-954 parameter will also be determined for C_{max} and AUC. The urinary PK parameters determined are A_{et} , f_e , and CL_r . Descriptive statistics (N, mean, SD, CV%, median, minimum and maximum) will be used to summarize the PK parameters for TAK-954 (and metabolites THRX-513466 and THRX-913682) by regimen. In addition, geometric mean will be computed for C_{max} and AUC parameters. Additional plasma and/or urine PK parameters may be calculated if necessary, in accordance with the Clinical Pharmacology Analysis Plan (CPAP). All pharmacokinetic parameters calculated will be provided in a data listing.

Box plots for C_{max} and AUC_{∞} will be generated by regimen.

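### The SAP's rule that plasma values below LLOQ count as zero has no exception for wholly unquantifiable profiles, so planned metabolite geometric means may become zero or undefined (minor; primary comparison essentially unaffected)

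*SAP*

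**What the plan says.** - SAP 7.1.6 (Conventions for Missing Data): plasma concentrations below the LLOQ "will be treated as zero in the summarization of concentration values and derivation of PK parameters". The sentence covers plasma only. It does not separate values before the first quantifiable sample, values after the last one, and profiles with no quantifiable sample.
- SAP 7.9.1 plans parameter summaries by regimen for TAK-954 and the metabolites THRX-513466 and THRX-913682, and metabolite-to-parent ratios for Cmax and AUC. It then states: "In addition, geometric mean will be computed for C_{max} and AUC parameters". Concentrations by time point get arithmetic descriptive statistics and mean plots on linear and semi-log axes. The paired t-tests are on log Cmax, AUC-infinity and AUClast of TAK-954.
- SAP 5.0 defines the primary AUC-infinity as "calculated using the observed value of the last quantifiable concentration". The SAP abbreviation list ends AUClast at the last measurable time point.
- Protocol 6.2.1, on two active metabolites after oral dosing, reports that mean Cmax and 0-to-48-hour AUC "metabolite to parent ratios ranged from 0.0008 to" 0.004.
- Neither document gives an LLOQ for any analyte.

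**The concern.** The zero rule and the planned metabolite summaries do not fit together. If a subject has no quantifiable metabolite sample, the rule turns an unknown small exposure into an exact zero. One zero makes a regimen's geometric mean zero in product form and undefined in log form. That subject's metabolite-to-parent ratio becomes 0. If the metabolite was just above LLOQ with TAK-954 alone and just below it with itraconazole, the table would show complete suppression.

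There are two smaller effects. Read literally, the rule puts a zero after the last quantifiable sample into the AUC calculation, where the SAP's own AUC definitions stop. And if itraconazole slows elimination, TAK-954 alone falls below LLOQ first, so zeros pull down its late means more and enlarge the contrast in the mean profiles.

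**Working it through.** No figure in the plan depends on this rule, so there is nothing to reproduce. The check is how far each output moves over a range of assumed LLOQs.

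**Inputs from the documents:** metabolite-to-parent ratio 0.0008 to 0.004 and half-life 18.0 to 18.9 h (Protocol 6.2.1); last sample at 120 h (SAP 7.9.1); about 10 subjects and a log-scale SD of 0.129 for AUC (SAP 6.0).

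**Assumptions:** LLOQ from 0.02% to 5% of parent Cmax; log-scale between-subject SD of 0.3 for metabolite Cmax; oral ratios carry over to the IV dose and to the two metabolites named in the SAP; half-life 18.5 h alone and 18.5 × 1.5 = 27.75 h with itraconazole.

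**1. Metabolite profile wholly below LLOQ**

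For one subject, p = Φ(ln(LLOQ/metabolite Cmax)/0.3), both as fractions of parent Cmax. For at least 1 of 10, P = 1 − (1 − p)^10.

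Example, ratio 0.0008 and LLOQ 0.05%: ln(0.0005/0.0008)/0.3 = −1.567, p = 0.0586, P = 1 − 0.9414^10 = 45%.

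| Ratio | LLOQ (% of parent Cmax) | P(at least 1 of 10) |
|---|---|---|
| 0.0008 | 0.02 / 0.05 / 0.1 | 0% / 45% / 100% |
| 0.002 | 0.05 / 0.1 / 0.2 | 0% / 10% / 99.9% |
| 0.004 | 0.1 / 0.2 / 0.5 | 0% / 10% / 100% |

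The assumed SD matters near the threshold. With SD 0.2, the example gives z = −2.35, p = 0.0094, P = 9%. With SD 0.4, it gives z = −1.175, p = 0.120, P = 72%.

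An assay adequate for the parent need not be adequate here. With one-phase decay from the end of infusion, the parent at 120 h is 2^(−119/18.0) = 1.0% to 2^(−119/18.9) = 1.3% of Cmax. A shared LLOQ between 0.4% and 1.0% of parent Cmax would follow a typical parent profile to 120 h and miss a typical metabolite profile entirely. Protocol 6.2.1 describes biphasic decline, which would put the late parent level lower and narrow that window.

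**2. Literal trailing zero in the primary AUC-infinity**

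With one-phase decay from a peak at time 0, the added triangle as a share of AUC-infinity is k × (Δt/2) × exp(−k × tlast), with Δt = 24 h. k = ln 2/18.5 = 0.0375 alone and ln 2/27.75 = 0.0250 with itraconazole. Alone, the level is 6.7%, 2.7% and 1.1% of peak at 72, 96 and 120 h. With itraconazole it is 16.6%, 9.1% and 4.99%.

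| LLOQ (% of peak) | tlast alone / with itraconazole | Added alone / with itraconazole | Change in ratio |
|---|---|---|---|
| 1 | 120 / 120 h | 0 / 0 | 0 |
| 2 | 96 / 120 h | 1.2% / 0 | 1/1.012 − 1 = −1.2% |
| 3 to 4 | 72 / 120 h | 3.0% / 0 | 1/1.030 − 1 = −2.9% |
| 5 | 72 / 96 h | 3.0% / 2.7% | 1.027/1.030 − 1 = −0.3% |

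The shift is 0 to about −3%, and downward. If trailing values are left out, the simulation in step 3 gives a stable AUC-infinity ratio over LLOQs of 0.1% to 5% of Cmax: 1.485 to 1.493 with one-phase decay and 1.386 to 1.407 with two-phase. In that simulation a literal trailing zero moves the AUClast ratio by at most about 2.5% (1.508 to 1.470 at LLOQ 5%). Cmax does not depend on the rule.

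**3. Late-time mean concentrations**

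Ratio of arithmetic means at 120 h (itraconazole over alone), from 300 simulated trials of 10 subjects:

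| Decay | LLOQ (% of Cmax) | True | Zero rule |
|---|---|---|---|
| One-phase | 0.1 / 1 / 2 | 4.27 / 4.25 / 4.24 | 4.27 / 5.44 / 15.1 |
| Two-phase | 0.1 / 0.5 / 1 | 4.24 / 4.23 / 4.24 | 4.25 / 11.1 / 88 |

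With one-phase decay and LLOQ 1%, 40% of the alone samples and none of the itraconazole samples are below LLOQ. A regimen mean of zero also cannot be drawn on a semi-log axis.

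**The case against.** The strongest defence is that nothing confirmatory depends on the rule. The AUC definitions already stop at the last quantifiable or measurable sample. No test by time point is planned, and medians and individual listings will show where values fall below LLOQ. Metabolite assay is itself conditional in the study design text. Protocol 11.1.1 limits parameter summaries to valid estimates, and non-compartmental detail is deferred to a clinical pharmacology analysis plan that is not among the documents. With a sensitive enough assay nothing happens at all.

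Most of this stands and sets the severity. It does not remove the point. SAP 7.1.6 makes the zero a derived value, so nothing in the SAP marks it as invalid. The PK set in SAP 7.2 does not repeat the valid-estimates sentence, and 7.1.6 does not defer to the other plan.

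The defence also has a fair point about the remedy. Averaging only calculable metabolite values drops the lowest exposures and biases the mean upward, which could hide suppression. Showing n alone does not correct that.

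A reader might infer that the primary AUC is at risk, because a trailing triangle of 1% to 9% of AUC-infinity within a regimen looks large beside the standard error of the log ratio, 0.129/√10 = 4.1%. The documents do not support this. The comparison is paired, so only the net change in the ratio counts. The largest triangles (7.4% alone, 9.0% with itraconazole, both with tlast 48 h) need an LLOQ above 6.7% and 16.6% of peak, and nothing in the documents suggests such an assay.

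**Conclusion.** The point holds as a minor one, on secondary and descriptive outputs. The zero rule conflicts with the planned metabolite geometric means whenever a profile is wholly below LLOQ, and the protocol's own metabolite ratios make that foreseeable. It is not certain: the probability runs from 0% to 100% over the LLOQs tried, and it rests on the assumed SD and on oral ratios applying to the IV dose. The metabolite-to-parent ratio would become zero, not undefined. The undefined quantities are the log-form geometric mean and the metabolite AUC-infinity.

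Read literally, the rule also contradicts the SAP's AUC definitions. The primary Cmax comparison is untouched, and the primary AUC-infinity comparison is essentially untouched if those definitions are followed. Distortion of late-time means is possible but confined to descriptive tables and plots.

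A reader might also take the metabolite ratios to be the plan's main evidence on metabolite formation. The documents do not say so: the primary objective concerns TAK-954, and the exploratory objectives are redacted.

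**What to change.** Amend SAP 7.1.6 so that:

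1. Values below LLOQ before the first quantifiable sample are zero.
2. Values below LLOQ after the last quantifiable sample are excluded from AUC and terminal-slope derivation, in line with SAP 5.0.
3. Zero may be kept for concentration summaries, with the number below LLOQ shown at each time point and on the mean plots.
4. Parameters and ratios from a wholly unquantifiable metabolite profile are reported as not calculable (<LLOQ), not zero. Geometric means use calculable values, with n and the number below LLOQ by regimen, and a note that leaving out those subjects biases the metabolite mean upward.

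The change is to SAP wording only and leaves the primary analysis as planned. The cost is that some metabolite parameters will be blank, and the remaining metabolite means must be read alongside the counts below LLOQ.

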7.2 Analysis Sets

The following analysis sets will be used for analysis and presentation of the study data:

- Safety Analysis Set: The safety analysis set will consist of all subjects who are randomized and received at least 1 dose of study drug. Subjects in this analysis set will be used for demographic, baseline characteristics, and safety summaries.
- Pharmacokinetic Set: The PK set will consist of all subjects who received at least 1 dose of study drug and have at least 1 measurable plasma concentration.

If any subjects are found to be noncompliant in dosing schedule or with incomplete data, a decision will be made on a case-by-case basis as to their inclusion in the analysis but will be presented in the subject listings.

Number of subjects in each analysis set will be tabulated.

7.3 Disposition of Subjects

Study Information, including date of first subject signing Informed Consent Form (ICF), date of first/last study drug, date of last subject's last visit/contact, date of last subject's last procedure for collection of data for primary endpoint, Medical Dictionary for Drug Regulatory Activities (MedDRA) Version, World Health Organization Drug Dictionary (WHODrug) Version, and SAS Version, will be tabulated.

The eligibility of subjects will be summarized, along with the primary reasons of screen failure as recorded in eCRF.

Disposition of all enrolled subjects will be tabulated. Categories will include:

- Subjects who completed the study
- Subjects who prematurely discontinued study

Primary reasons for discontinuing study, as entered on the eCRF will be tabulated.

7.4 Demographic and Other Baseline Characteristics

Demographic and study baseline characteristics, including age at informed consent, gender, ethnicity, race, height (cm), weight (kg) and body mass index (kg/m²), will be summarized.

There will be no inferential analysis of demographic and baseline characteristics.

7.5 Medical History and Concurrent Medical Conditions

Medical history is defined as significant conditions or diseases that resolved at or prior to the time of informed consent. Concurrent medical conditions are defined as significant conditions or diseases that are present at signing of informed consent.

Medical history and concurrent medical conditions will be coded using the MedDRA coding system.

Medical history and concurrent medical conditions will be listed by site and subject number.

There will be no summary or inferential analysis of medical history and concurrent medical conditions.

7.6 Medication History and Concomitant Medications

Medication history information includes any medication relevant to eligibility criteria stopped at or within 28 days prior to signing of informed consent. Concomitant medication is any drug given in addition to the study drug, taken at any time from signing of informed consent through the end of study.

Medication history and concomitant medications will be coded using the WHODrug.

Listings for medication history and concomitant medications will be produced by site and subject number.

There will be no summary or inferential analysis of medication history and concomitant medications.

7.7 Study Drug Exposure and Compliance

All doses of study medication will be at the clinic. Dosing data, including dosing time will be provided by subject and visit in the listings.

Daily meals during confinement in each period will be reported in the data listings.

7.8 Efficacy Analysis

Not applicable.

7.9 Pharmacokinetic/Pharmacodynamic Analysis

7.9.1 Pharmacokinetic Analysis

Blood samples for PK analysis of TAK-954 are obtained relative to the dose on Day 1 of Period 1 and Day 4 of Period 2 at the following times: predose (within 30 minutes), and 0.33, 0.5, 0.67, 1 (just after the end of infusion), 1.5, 2, 3, 4, 6, 12, 24, 36, 48, 72, 96, and 120 hours postdose (relative to TAK-954 start of infusion).

The concentration of TAK-954 (and metabolites THRX-513466 and THRX-913682) in plasma will be summarized by regimen over each scheduled sampling time point using descriptive statistics (arithmetic mean, SD, CV%, median, minimum and maximum). Individual plasma concentration data versus time will be presented in a data listing.

In addition, the figures for mean plasma concentrations of TAK-954 (and any measured metabolites) versus time (linear and semi-log scale) will be generated.

Urine is collected at predose, 0 to 6, 6 to 12, 12 to 24, and 24 to 48 hours relative to TAK-954 infusion start in Trial Periods 1 and 2. The amount of TAK-954 (and any measured metabolites) recovered in urine will be summarized by regimen over each scheduled sampling interval using descriptive statistics (arithmetic mean, SD, CV%, median, minimum and maximum). Individual urine collection information including volume, concentration, and amount recovered will be presented in a data listing.

The plasma PK parameters determined are C_{max} , AUC_{∞} , AUC_{last} , $t_{1/2}$, CL, and V_z . The ratio of metabolite parameter to TAK-954 parameter will also be determined for C_{max} and AUC. The urinary PK parameters determined are A_{et} , f_e , and CL_r . Descriptive statistics (N, mean, SD, CV%, median, minimum and maximum) will be used to summarize the PK parameters for TAK-954 (and metabolites THRX-513466 and THRX-913682) by regimen. In addition, geometric mean will be computed for C_{max} and AUC parameters. Additional plasma and/or urine PK parameters may be calculated if necessary, in accordance with the Clinical Pharmacology Analysis Plan (CPAP). All pharmacokinetic parameters calculated will be provided in a data listing.

Box plots for C_{max} and AUC_{∞} will be generated by regimen.

For evaluation of potential effect of itraconazole on TAK-954 PK, paired t-tests and associated CIs will be determined on the natural logarithms of C_{max} and area under the concentration-time curve (AUC_{∞} and AUC_{last}) to assess the exposure between regimens (TAK-954 alone and TAK-954 with itraconazole). This paired t-test (one-sample t-test) will be performed on the differences (TAK-954 with itraconazole minus TAK-954 alone) of the natural logarithm transformed parameters for the two regimens. The relative bioavailability estimate and the 90% confidence intervals for relative bioavailability will be obtained by exponentiating the estimated difference and the 90% confidence intervals for the estimated difference between regimens in the log-transformed parameters.

Additional analyses may be performed if appropriate.

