11.1.3 PK Analysis

Concentrations of TAK-954 and any measured metabolites will be summarized by regimen over each scheduled sampling time using descriptive statistics.

The amount of TAK-954 and any measured metabolites excreted in urine will be summarized by regimen using descriptive statistics.

Individual plasma and urine concentration versus time data will be presented in a data listing.

Plasma and urine PK parameters of TAK-954 and any measured metabolites will be summarized by regimen using descriptive statistics.

For evaluation of potential effect of itraconazole on TAK-954 PK, paired t-tests and associated CIs will be determined on the natural logarithms of C_{\max} and area under the concentration-time curves to assess the exposure between regimens (TAK-954 alone and TAK-954 with itraconazole). The geometric mean of the relative bioavailability of the TAK-954 with itraconazole regimen relative to the TAK-954 alone regimen and the associated 90% CIs will be determined by exponentiating the appropriate estimates for the difference between regimens in the log-transformed parameters.

A more detailed analysis will be presented in the SAP. Additional analyses will be included, if appropriate.

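### The trial is sized on a 95% confidence interval excluding 1.25, but the analysis reports a 90% interval and a paired t-test and never refers to 1.25

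*SAP*

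**What the plan says.** **Sizing.** SAP Section 6.0, repeated in Protocol Section 11.3 and the trial summary, bases the sample size on "a 2-sided 95.0% CI for the geometric mean ratio of Cmax for TAK-954 when administered with and without itraconazole". With 10 completers this interval "will have 90% probability of excluding 1.25 (the upper bound of the bioequivalence range") if the true increase in Cmax is at least 50%. The stated inputs are a distance of 0.182 from the mean to the lower limit on the log scale and an SD of log differences of 0.187. For AUC∞, an SD of 0.129 is used and the stated probability is above 99%.

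**Analysis.** The primary endpoints are Cmax and AUC∞ (SAP Section 5.0). SAP Section 7.9.1 plans a paired t-test on log-transformed values: "This paired t-test (one-sample t-test) will be performed on the differences (TAK-954 with itraconazole minus TAK-954 alone"). It then says "the 90% confidence intervals for relative bioavailability will be obtained by exponentiating the estimated difference" and its 90% limits. Protocol Section 11.1.3 agrees: "the associated 90% CIs will be determined by exponentiating the appropriate estimates". Neither section gives a null value, a significance level, a reference bound or a rule for reading the result.

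**General conventions.** SAP Section 7.1 says that, where applicable, "p-values will be rounded to 3 decimal places prior to assessment of statistical significance". No significance level appears in either document.

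**The concern.** A sample-size statement should describe what the analysis will do. Here the two differ in confidence level (95% against 90%) and in reference value (1.25 against, by default, 1.0). The probability quoted for the design therefore belongs to an interval that the analysis does not name and a comparison that it does not make.

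Two things are at stake. First, a result near the boundary may exclude 1.25 at one level and not at the other, and the plan does not say which counts. Second, 1.25 is the only bound that the documents treat as relevant, yet it is missing from the analysis. How the size of the effect is to be described is thus left open until the data are seen, in an open-label trial.

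**Working it through.** **Inputs** (SAP 6.0 and Protocol 11.3): n = 10; true ratio 1.5; bound 1.25; SD of log differences 0.187 for Cmax and 0.129 for AUC. The 0.129 is taken as an SD of differences, parallel to Cmax. Critical values on 9 df: t = 2.262 (95%) and t = 1.833 (90%).

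**1. The plan's own figure.** The distance 0.182 is ln(1.5/1.25) = 0.1823. Read as an interval-width calculation for Cmax:
- P(half-width ≤ 0.182) = P(χ²₉ ≤ 9 × [0.182√10 / (2.262 × 0.187)]²) = P(χ²₉ ≤ 16.66) = 94.6%. With n = 9 it is 88.2%, so 10 is the smallest n that reaches 90%.
- P(half-width ≤ 0.182 and the interval covers the true mean) = 89.6%, which reproduces 90%.

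For AUC the half-width probability is 99.99%, consistent with above 99%; the joint version gives 95.0%. If 0.129 were a within-subject SD, the SD of differences would be 0.129 × √2 = 0.182 and the half-width probability 95.9%. The plan's above-99% figure therefore favours reading 0.129 as the SD of differences.

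**2. The event the text describes.** The probability that the lower limit exceeds 1.25 at a true ratio of 1.5 is P(T > t), where T is noncentral t on 9 df with noncentrality δ = 0.1823 × √10 / SD. This gives δ = 3.083 for Cmax and 4.469 for AUC.

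| | 95% interval | 90% interval |
|---|---|---|
| Cmax, SD 0.187 | 78.3% | 88.4% |
| AUC, SD 0.129 | 97.7% | 99.3% |

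**3. Where the two levels disagree.** For an observed SD of 0.187, the 90% interval excludes 1.25 when the observed ratio exceeds 1.25 × exp(1.833 × 0.187/√10) = 1.393. The 95% interval needs 1.25 × exp(2.262 × 0.187/√10) = 1.429. Over repeated trials at a true ratio of 1.5, disagreement occurs in 88.4% − 78.3% = 10.1% for Cmax and 99.3% − 97.7% = 1.6% for AUC.

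**4. Illustration of the different reference values.** This needs two assumptions that the documents do not supply: a two-sided 5% test, and a lower bound of 0.80 to go with 1.25. The table gives simulated probabilities that p < 0.05 against 1.0 and that the 90% interval also lies inside 0.80–1.25 (10% test in brackets).

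| True ratio | AUC, SD 0.129 | Cmax, SD 0.187 |
|---|---|---|
| 1.10 | 45% (59%) | 10% (17%) |
| 1.12 | 51% (62%) | 11% (17%) |
| 1.15 | 47% (53%) | 10% (16%) |

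For an observed AUC SD of 0.129, both results occur for observed ratios between exp(2.262 × 0.129/√10) = 1.097 and 1.25 × exp(−1.833 × 0.129/√10) = 1.160. For example, a ratio of 1.12 gives p = 0.021 and a 90% interval of 1.039 to 1.207. For Cmax with an observed SD of exactly 0.187, the test needs a ratio above 1.143 and containment needs one below 1.122, so both cannot occur at 5%. They can if the observed SD falls below 0.172, which has a 43% chance when the true SD is 0.187.

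**The case against.** The primary objective is to evaluate an effect, which is estimation. The ratio and its 90% interval will be reported, so any reader can see the size of the effect and apply a bound. This stands, and it limits the harm: the estimates are unaffected.

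A reader might infer that the plan can produce contradictory conclusions, a significant interaction and an effect inside the bioequivalence range. The documents do not support that. A ratio can differ from 1.0 and still lie inside 0.80–1.25; these are answers to different questions. Nor do the documents call the t-test primary or write down a null of 1.0. The significance wording is in a general paragraph on decimal places, and SAP 7.9.1 itself contains no significance rule. The overlap is also mainly an AUC result.

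It can further be said that 1.25 is only a sizing reference, that 0.80 appears nowhere, and that choosing a no-effect range for TAK-954 is a pharmacological judgement. This is right as far as it goes. The sponsor has nevertheless already used 1.25 as the bound that matters, and should either carry it forward or say why not.

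A rule might be in the separate clinical pharmacology analysis plan, which was not available. However, Protocol Sections 11.1 and 11.1.3 assign the analysis methods to the SAP.

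**Conclusion.** The point holds as a mismatch between sizing and analysis. The 95% level and the bound of 1.25 that justify n = 10 do not appear in the planned analysis. At the planning scenario the change of level alone moves the Cmax probability from 78.3% to 88.4% and leaves about 10% of trials in which the two levels disagree about 1.25. These figures rest on the plan's SDs, 10 completers and normally distributed log differences.

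A reader might also infer that the trial is too small. That does not follow. The stated 90% reproduces as an interval-width calculation, and with the interval actually planned the probability of excluding 1.25 is about 88% for Cmax and 99% for AUC.

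The overlap figures of 45–51% for AUC and 10–11% for Cmax depend on the assumed 5% test and the assumed lower bound of 0.80. They show why the governing criterion should be stated; they do not show an error in the method. The change should be made, but the estimates are valid without it.

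**What to change.** 1. Use one confidence level and one bound in the trial summary, Protocol 11.3, SAP 6.0, Protocol 11.1.3 and SAP 7.9.1. With the planned 90% interval, restate the probability that the lower limit exceeds 1.25 at a true ratio of 1.5 as about 88% for Cmax and 99% for AUC. If 95% is kept, the figures are 78% and 98%, and the analysis must report that interval.
2. In SAP 7.9.1, state that the effect on each primary parameter is interpreted from the 90% interval of the geometric mean ratio relative to the bioequivalence range that the sizing cites. The upper bound is 1.25; the sponsor must confirm the lower bound, assumed here to be 0.80.
3. State that any p-value against 1.0 is descriptive.

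**Cost.** This is wording only: the 90% interval is already planned and n need not change. The stated Cmax figure falls slightly below 90%. Keeping a literal 90% would need n = 11 with a 90% interval (91.3%) or n = 14 with a 95% interval (92.0%; n = 13 gives 89.7%). Reading the interval against 0.80–1.25 will also often leave the effect unresolved: 76% (AUC) and 83% (Cmax) of trials at a true ratio of 1.20, and 77% and 84% at 1.30. The SAP should say that such results are reported as the ratio with its interval.
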